Validity of Bispectral index monitoring during deep sedation for botulinum toxin injection in
children with cerebral palsy

NCT02096549

[name], [name], PhD

Department of Anesthesiology and Pain Medicine, Yeungnam University School of Medicine, Daegu,
Republic of Korea

Address for Correspondence: [name], PhD

Department of Anesthesiology and Pain Medicine, School of Medicine, Yeungnam University, [name]
E-mail: [contact]([name])

Study Protocol

Document Date: April 30, 2017

Uploaded: June 10, 2018

This prospective observational study was approved by the institutional review board of Yeungnam medical center and was registered with ClinicalTrials.gov on the March 28, 2014 (NCT02096549). Written informed consent from parents and verbal assent from child, when appropriate, were obtained before enrollment of study. Twenty-two ASA physical status 1 and 2 children, aged between 3 and 18, with cerebral palsy (CP) scheduled for botulinum toxin injection under deep sedation were enrolled. Children were excluded from the study when either they had an anticipated difficult airway, unstable cardiac disease, craniofacial defect, allergy to drugs used

in this study and recent (< 8 week) history of pneumonia, bronchitis, asthma attack or upper respiratory infection.

No participant received premedication. A 22-gauge intravenous catheter was inserted at a superficial vein in arm or hand by an expert nurse 1 hour before estimated induction of sedation. On arrival of child with one of parents in the operating room, he/she was placed in supine position with a soft roll under his/her shoulder to slightly extend the neck. They were continuously monitored by electrocardiography, noninvasive blood pressure (NIBP) and pulse oximetry. An age and head size-appropriate bispectral index (BIS) sensor was applied to unilateral forehead and connected to a BIS monitoring system (VISTA™; Aspect Medical system, Newton, MA, USA) in accordance with the manufacturer's instruction. The BIS monitor screen was covered during the procedure to ensure that the anesthesiologist, who was responsible for induction and maintenance of sedation and analgesia, was blinded to the BIS value. All baseline data were collected before administration of remifentanil. Supplemental oxygen was administered by a simple face mask at a flow rate 5 L/min throughout procedure. Ventilation was monitored by respiratory rates per minute and continuous waveform of expired CO₂ using a sampling line, located around a nostril inside the face mask, connected to a side-stream capnography during sedation.

Before administration of propofol, remifentanil infusion at a rate of 0.05 µg/kg/min was started. Five minutes after start of remifentanil infusion, an attending anesthesiologist administered propofol (1 mg/kg) mixed with lidocaine (1 mg/kg) over 1 minute followed by continuous infusion of propofol on the basis of clinical signs of arousability, movement, blood pressure, heart rate and respiratory rate in a spontaneous breathing child. Two independent investigators assessed the level of sedation using the clinical sedation scale such as UMSS and the modified Observer's Assessment of Alertness/Sedation (MOAAS) every minute during induction and maintenance of sedation (Table 1). MOAAS includes only the responsiveness component of the original OAA/S (5). These two observers performing the clinical sedation score assessments were blinded to the BIS monitor throughout study period. Another third investigator recorded the BIS and EMG values, oxygen saturation, respiratory rate, blood pressure and heart rate immediately before each assessment of clinical sedation score. The BIS and EMG values with a signal quality index (SQI) ≥ 50 were accepted for analysis. Deep sedation was defined based on clinical sedation scale categories: a UMSS score of 3-4 or a MOAAS score of 0-1.

Statistical analysis plan

Document Date: April 30, 2017

Uploaded: June 10, 2018

The sample size was calculated with α error of 0.05 and a power of 80% to determine the validity of BIS values to detect deep sedation in children with cerebral palsy. A minimum 19 participants was required to detect a correlation coefficient of 0.6 for repeated measures. We enrolled 22 patients, taking into consideration of 15% drop-out rate.

Statistical analysis was performed with SPSS version 22.0 (SPSS Inc, Chicago, IL, USA) for Windows. Continuous variables were presented as mean \pm standard deviation for normal distributed data or the median and interquartile range for non-normal distributed data after the Kolmogorov-Smirnov test with Lilliefors correction. Categorical variables were presented as number of patients (%). The BIS values at each UMSS and MOAAS score were compared using one-way ANOVA followed multiple pairwise comparisons with Bonferroni correction. BIS values were categorized into ranges of <50, 50-59, 60-69, 70-79, 80-89 and 90 or higher. The Kappa was calculated to determine the agreement between the BIS value categories and clinical sedation score between 2 independent observers. A kappa ≥ 0.7 was considered good agreement. The correlation between the paired BIS value categories and clinical sedation scores was determined by Spearman rank correlation test. Receiver operating characteristic (ROC) curve analysis was performed to determine the sensitivity and specificity of BIS for predicting deep sedation based on clinical sedation scores. A cut-off BIS value for detecting deep sedation in children with CP was also calculated. A p value of 0.05 was considered to be statistically significant.

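### The ROC comparator is unrestricted, so awake readings are likely among the negatives and the AUC and specificity can overstate how well BIS separates deep from lighter sedation

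*Combined protocol and SAP*

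**What the plan says.** The Study Protocol states that no child is premedicated and that baseline data are taken before remifentanil. Remifentanil then runs alone for a time: "Five minutes after start of remifentanil infusion, an attending anesthesiologist administered propofol". Two observers score UMSS and MOAAS "every minute during induction and maintenance of sedation". BIS readings are accepted if the signal quality index is 50 or more; no other filter is stated. Deep sedation means UMSS 3 or 4, or MOAAS 0 or 1.

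The Statistical analysis plan compares BIS across the individual UMSS and MOAAS scores by ANOVA and then groups it: "BIS values were categorized into ranges of <50, 50-59, 60-69, 70-79, 80-89 and 90 or higher". It plans an ROC of BIS for deep sedation, and adds: "A cut-off BIS value for detecting deep sedation in children with CP was also calculated". It does not define the non-deep class, name a criterion for choosing the cut-off, or plan an ROC restricted to children who are already sedated.

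**The concern.** An ROC with one defined positive class and no exclusion beyond signal quality treats every other accepted reading as a negative. Scoring each minute through the induction of unpremedicated children should produce some readings at or near the awake state, and these are easy to tell from deep sedation.

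In a child already sedated, the harder and more useful question is whether BIS tells deep from lighter sedation. If many negatives are awake, the pooled AUC and specificity largely answer the easier question, and they change with the number of awake minutes that happened to be scored. A reader could then credit BIS, and the single published cut-off, with more ability to separate deep from moderate sedation than the data show.

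**Working it through.** **Figures in the plan.** The plan gives no expected AUC, cut-off or BIS distribution, so there is nothing of its own to reproduce here. Its sample size concerns a correlation ("A minimum 19 participants was required to detect a correlation coefficient of 0.6 for repeated measures") and does not bear on this point.

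**Number of pre-propofol readings.** If scoring starts with remifentanil, there are about 5 to 6 readings per child before propofol: 22 × 5 = 110 to 22 × 6 = 132. If scoring starts with propofol, there are few. The documents do not say which applies.

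**Effect on the AUC.** Let w be the awake share of the non-deep readings. The pooled AUC is an exact weighted average:

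AUC(w) = (1 − w) × AUC(deep v sedated) + w × AUC(deep v awake)

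For two normal levels, AUC = Φ[(μ non-deep − μ deep) / √(SD² non-deep + SD² deep)]. All BIS values below are assumptions. The five levels run from awake to deepest: one awake, two sedated but not deep, and two deep, with equal weights within the last two classes.

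*Scenario 1:* means 95, 85, 75, 62, 52; SDs 3, 8, 10, 12, 12.
- Deep v sedated, four pairs: Φ(23/14.42) = 0.945, Φ(13/15.62) = 0.797, Φ(33/14.42) = 0.989, Φ(23/15.62) = 0.930; mean 0.915.
- Deep v awake: Φ(33/12.37) = 0.996, Φ(43/12.37) = 1.000; mean 0.998.

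*Scenario 2:* means 95, 82, 72, 64, 56; SDs 3, 10, 12, 13, 13.
- Deep v sedated: Φ(18/16.40) = 0.864, Φ(8/17.69) = 0.674, Φ(26/16.40) = 0.944, Φ(16/17.69) = 0.817; mean 0.825.
- Deep v awake: Φ(31/13.34) = 0.990, Φ(39/13.34) = 0.998; mean 0.994.

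The gain is w × (AUC awake − AUC sedated), that is w × 0.083 in scenario 1 and w × 0.169 in scenario 2. Capping BIS at 98 in a simulation gives the same AUCs.

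| Awake share | Scenario 1: AUC (gain) | Scenario 2: AUC (gain) |
|---|---|---|
| 0% | 0.92 | 0.83 |
| 10% | 0.92 (+0.01) | 0.84 (+0.02) |
| 25% | 0.94 (+0.02) | 0.87 (+0.04) |
| 50% | 0.96 (+0.04) | 0.91 (+0.08) |
| 75% | 0.98 (+0.06) | 0.95 (+0.13) |

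**Effect on specificity at a fixed cut-off.** Pooled specificity is averaged in the same way. In scenario 2, with the cut-off set for 90% sensitivity, specificity is 0.50 among sedated readings and 1.00 among awake readings. At w = 50% the pooled figure is 0.5 × 0.50 + 0.5 × 1.00 = 0.75, while the figure among sedated readings stays at 0.50. The cut-off itself does not move, because it depends on deep readings only.

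**Effect on a Youden cut-off (simulated, same assumptions).** From 0% to 50% awake, the cut-off goes from 69 to 73 in scenario 1 and from 69 to 76 in scenario 2. Specificity among sedated readings falls from 0.85 to 0.76 and from 0.75 to 0.55. Sensitivity rises in exchange, in scenario 2 from about 0.75 to about 0.87. At 25% awake the cut-off moves by only about 1.5 and 2.5 points. The Youden maximum is flat, so repeat runs differ by up to 1.5 BIS points and 0.05 in specificity.

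**Other assumed values.** With deep 55 (SD 12), light or moderate 70 (SD 12) and awake 95 (SD 4), the two component AUCs are Φ(15/16.97) = 0.81 and Φ(40/12.65) = 0.999, which gives 0.91 at 50% awake. Across four such sets, going from 0% to 50% awake raised the AUC by 0.03 to 0.14 and the Youden cut-off by 4 to 10 points. The direction was the same in every set.

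**The case against.** The strongest reply is that the stated aim is to detect deep sedation, and deep versus any other state over induction and maintenance is a legitimate target. For that target the pooled AUC is not biased; it depends on the mix of readings. This stands, and is why the all-readings ROC should stay.

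A reader might infer that pre-propofol minutes are definitely in the analysis. The documents do not support that. The start of induction is not defined, the scoring sentence follows the description of the propofol bolus and infusion, and baseline data are described separately with no statement that they enter the ROC. The top BIS category is the end of a grouping scheme and does not count awake readings.

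A reader might also infer that the published cut-off must be too high, so that moderately sedated children would be called deeply sedated. That needs a Youden-type rule. The plan names none, and a fixed-sensitivity rule would leave the cut-off where it is.

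Two further objections carry weight. Nothing in the documents points to an awake share as high as 50% or 75%, and at 10% the effect is small. The plan also compares BIS between individual scores with Bonferroni-corrected pairwise tests, so moderate and deep readings are contrasted. Those tests compare means, however, and give no specificity by level; they narrow the gap without closing it.

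Finally, a restricted ROC selects readings by the reference score and would drop awake-scored readings that are real data. That argues for adding it, not for replacing the planned one.

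**Conclusion.** The concern holds in limited form. No text restricts the comparator, and awake or near-awake readings are likely among the negatives. The AUC and pooled specificity then depend on how many such minutes were scored, whatever cut-off rule is used, and can overstate the separation of deep from lighter sedation. An upward shift of the cut-off follows only under a Youden-type rule.

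The size cannot be derived from the documents. In the two main scenarios the AUC gain is about 0.01 to 0.02 at 10% awake and 0.04 to 0.08 at 50%. This rests on assumed BIS means and SDs, equal weights within the sedated and deep classes, and awake values close to 95.

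The point is worth acting on because it changes what the study can conclude about deep versus lighter sedation, and the data needed are already recorded.

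**What to change.** In the Statistical analysis plan:
- Keep the all-readings ROC for the stated target, and say that every accepted non-deep reading is a negative.
- Add a pre-specified ROC, with AUC, sensitivity, specificity and cut-off, for deep versus sedated-but-not-deep readings, excluding the fully awake score on each scale (leaving UMSS 1–2 and MOAAS 2–4 as the comparators). If results have already been seen, label it as added afterwards.
- Report the number of readings and the specificity at the chosen cut-off for each non-deep score level.
- State when scoring starts relative to remifentanil and propofol, whether baseline readings enter the ROC, and the criterion for choosing the cut-off.
- Limit any conclusion about separating deep from lighter sedation to the restricted result.

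The cost is a few lines of text and one more ROC per scale on existing data. The restricted analysis has fewer non-deep readings, so its interval will be wider and its AUC probably less favourable.

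### Minute-by-minute BIS readings from 22 children are analysed with no within-child method, so p values and any intervals will usually be too optimistic

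*Combined protocol and SAP*

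**What the plan says.** In the Study Protocol, two observers score sedation (UMSS and MOAAS) "every minute during induction and maintenance of sedation". A third investigator records BIS "immediately before each assessment of clinical sedation score". Values that pass the signal-quality threshold enter the analysis. Each child therefore yields a run of BIS-score pairs about a minute apart. Neither the number of pairs per child nor any within-child correlation is given.

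The analysis paragraph of the Statistical analysis plan lists the methods:
- "The BIS values at each UMSS and MOAAS score were compared using one-way ANOVA", with Bonferroni pairwise comparisons.
- "The correlation between the paired BIS value categories and clinical sedation scores was determined by Spearman rank correlation test".
- ROC "curve analysis was performed to determine the sensitivity and specificity of BIS for predicting deep sedation", after which "A cut-off BIS value for detecting deep sedation in children with CP was also calculated".

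It sets a significance threshold of 0.05. It mentions no mixed model, GEE, clustered variance, resampling of children or per-child summary.

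The sample-size paragraph gives alpha 0.05 and 80% power, then "A minimum 19 participants was required to detect a correlation coefficient of 0.6 for repeated measures", then "We enrolled 22 patients, taking into consideration of 15% drop-out rate". Its stated purpose is the validity of BIS for detecting deep sedation, but its only numerical target is the correlation.

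**The concern.** The ANOVA groups BIS values by sedation score, not by child, so the reading is the unit of analysis. No per-child summary is described for the Spearman and ROC analyses either, so pooling all readings is the natural interpretation. Standard versions of all three methods assume independent observations. Readings a minute apart in one child are not independent: they share that child's characteristic BIS level, and neighbouring minutes resemble each other. A few hundred pooled readings can then pass for a few hundred independent ones when there are only 22 children.

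At stake is the study's main product, a BIS threshold for deep sedation in children with cerebral palsy. Its AUC, sensitivity, specificity and supporting p values could look firmer than 22 children can support. The repeated-measures wording in the sample-size paragraph might reassure a reader that this was handled, but nothing in the analysis paragraph does so.

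**Working it through.** **1. The plan's own figure of 19.** From the sample-size paragraph: alpha 0.05, power 80%, r = 0.6. Assumed, because not stated: two-sided test, null correlation 0, one independent pair per child.
- Fisher z: n = ((1.960 + 0.842) / atanh(0.6))² + 3 = (2.802 / 0.693)² + 3 = 19.34.
- Exact power under bivariate normality: 79.0% at n = 18 and 81.4% at n = 19.

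So 19 is the smallest n reaching 80%, with no repeated-measures input. Other routes can also arrive near 19. A within-child correlation with error degrees of freedom N(k-1)-1 needs 18 to 19 children at k = 2 readings. A design-effect formula, N = 19(1 + (k-1)ICC)/k with k = 10, gives 3.6, 7.0, 10.5 and 18.1 at ICC 0.1, 0.3, 0.5 and 0.95; the last rounds up to 19. The actual derivation is unknown.

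**2. The drop-out allowance.** 19 × 1.15 = 21.85, which rounds to 22. Dividing instead gives 19/0.85 = 22.35, and 22 × 0.85 = 18.7. In whole children, three losses (3/22 = 13.6%) leave 19 and four (4/22 = 18.2%) leave 18.

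**3. What ignoring the child does to an AUC interval.** The documents supply only the 22 children; every other input here is assumed. True AUC is 0.85, with k = 10, 20 or 30 readings per child.

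*Model A.* The deep state is a latent normal variable with a child effect, cut at 0, so half the readings are deep. The BIS signal is 1.466 × deep + child effect + noise, with child effect and noise totalling variance 1. The same within-child correlation applies to state and signal. 3,000 runs per cell.

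*Model B.* Every child gives equal blocks of light and deep readings, with child effect 0.3 and first-order serial correlation. 2,000 runs per cell.

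Coverage of pooled 95% (DeLong) intervals:

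| Scenario | k = 10 | k = 20 | k = 30 |
|---|---|---|---|
| A, correlation 0 | 95.0% | 94.5% | 95.3% |
| A, 0.1 | 93.8% | 92.9% | 92.3% |
| A, 0.3 | 87.2% | 81.4% | 74.8% |
| A, 0.5 | 75.6% | 64.3% | 55.0% |
| A, 0.3 in BIS only (2,000 runs) | 92.4% | 89.2% | 88.7% |
| B, serial correlation 0 | 95.1% | 93.6% | 90.1% |
| B, 0.5 | 85.2% | 81.8% | 79.8% |
| B, 0.8 | 81.4% | 69.4% | 64.2% |

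**4. What a child-level interval does.** In Model A, clustered DeLong components with t on 21 degrees of freedom cover 92.3 / 93.2 / 92.4% at correlation 0.3 and 90.4 / 90.5 / 90.0% at 0.5. At k = 20 the mean half-width rises from 0.035 (pooled) to 0.053 at correlation 0.3 (0.053/0.035 = 1.5 times) and 0.074 at 0.5 (2.1 times). A percentile bootstrap of children at k = 20 (400 runs, 300 resamples) covers 90.0% and 90.5%; the simulation standard error is about √(0.9 × 0.1/400) = 1.5 percentage points.

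**The case against.** **The worst figures come from an unfavourable model.** Model A lets some children stay mostly deep or mostly light. The protocol describes baseline data followed by scoring through induction and maintenance, so most children should contribute both states. This stands. Model B is closer to the design, and with no serial correlation its pooled intervals are near nominal up to 20 readings. When every child contributes to both scores, part of the child effect cancels, and an ANOVA that ignores it can even be conservative. But Model B with serial correlation 0.8 still falls to 64-81%. That value is itself assumed.

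**The plan promises no confidence intervals.** True: it names a p-value threshold. The same independence assumption lies behind the ANOVA and Spearman p values, so the fix has to reach those as well as the ROC results.

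**Stronger readings of the sample-size paragraph.** A reader might infer that 19 is an arithmetic error. It is not: it is correct for one pair per child, and some repeated-measures inputs also give it. A reader might infer from 18.7 that 22 fails to cover a 15% loss. That is an expected value; any whole-child loss of 15% or less means at most three children, which leaves 19. The difference between multiplying and dividing is a convention worth less than one child. A reader might also infer that the ROC is underpowered because it has no target of its own. Sizing on one listed analysis is ordinary practice, and no ROC requirement is stated against which it could fall short.

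**The power check uses Pearson, but the plan uses Spearman on BIS categories.** This stands. Simulated Spearman power with one continuous pair per child is about 74% at 19 and 81% at 22. Since each child supplies many pairs, neither calculation describes the planned analysis. The Pearson figures only show what 19 is consistent with.

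**Conclusion.** The point holds as a gap in the analysis method. Serial readings are taken in each child, and the ANOVA, Spearman and ROC/cut-off analyses are named with no within-child term. Followed literally, the plan gives p values and any intervals that will usually be too optimistic.

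Confidence is high in the omission and low in its size. Under the assumed inputs, pooled 95% AUC coverage runs from about 95% (balanced light and deep readings, few readings, no serial correlation) to about 55-65% (strong correlation, 30 readings). The documents do not give the readings per child, the within-child correlation or the serial correlation that would place this study in that range, so a claim that the results are badly misleading would go too far.

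The sample-size matters are minor wording: an unsupported repeated-measures label, 80% power that refers only to the correlation, and a loosely stated drop-out allowance. They do not show that the study is too small.

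**What to change.** In the analysis paragraph of the Statistical analysis plan:
1. Replace the one-way ANOVA with a mixed model or GEE with child as the cluster. Allow for correlation between neighbouring minutes, use a small-sample correction suited to 22 clusters, and keep the Bonferroni pairwise comparisons.
2. Report the Spearman coefficient, AUC, sensitivity, specificity and cut-off with child-level confidence intervals, for example a bootstrap that resamples whole children and re-selects the cut-off in each resample. Base the Spearman inference on that interval instead of the pooled p value.
3. Report the number of accepted readings per child.

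In the sample-size paragraph, reword only:
1. Give the readings per child and within-child correlation behind 19, or drop the repeated-measures label and describe 19 as a one-pair-per-child figure.
2. Say that the 80% power refers to the correlation only.
3. Say that 22 allows for up to three losses (13.6%).

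The cost is some reanalysis of data already collected, with no added patients. Intervals will usually be wider: 1.3 to 2.5 times as wide in Model A at correlations 0.3 to 0.5. With 22 children the bootstrap is itself approximate (about 90% coverage for a nominal 95%), and the report should say so.

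### One-way ANOVA and ordinary Spearman tests are planned on minute-by-minute readings from 22 children with no allowance for child, so their p values are not valid; no interval is planned for ROC or kappa

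*Combined protocol and SAP*

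**What the plan says.** The Study Protocol section has two observers score each child "every minute during induction and maintenance of sedation". A third investigator records BIS "immediately before each assessment of clinical sedation score". The only stated filter is signal quality: "The BIS and EMG values with a signal quality index (SQI) ≥ 50 were accepted for analysis". Nothing reduces the readings to one value per child.

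The Statistical analysis plan section compares BIS across scores as follows: "The BIS values at each UMSS and MOAAS score were compared using one-way ANOVA followed multiple pairwise comparisons with Bonferroni correction". For association it says: "The correlation between the paired BIS value categories and clinical sedation scores was determined by Spearman rank correlation test". The threshold is general: "A p value of 0.05 was considered to be statistically significant". On accuracy it says: "Receiver operating characteristic (ROC) curve analysis was performed to determine the sensitivity and specificity of BIS for predicting deep sedation". A BIS cut-off is also derived, and kappa is judged against a point value of 0.7. No interval is mentioned for any of these.

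Repeated data are acknowledged once, in the sample-size paragraph: "A minimum 19 participants was required to detect a correlation coefficient of 0.6 for repeated measures". No named analysis takes this up.

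**The concern.** One-way ANOVA and the ordinary Spearman test both assume independent observations. Readings a minute apart in one child are not independent: the child has a characteristic BIS level, and successive values resemble each other. The plan has no child term, cluster-robust error, resampling of children or per-child summary. Bonferroni corrects for the number of contrasts, not for dependence.

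The aim is to learn whether, and at what BIS value, deep sedation is detected. If the p values can be too small or too large, a reader cannot correct them. This matters even if BIS clearly falls with sedation overall, because the pairwise contrasts include neighbouring scores that may not differ. The accuracy measures are a separate point. The plan attaches no specific p value to them and their point estimates remain usable as descriptions, but the reader gets no interval, or a software default that ignores the child.

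**Working it through.** **1. The plan's own figure.** Inputs from the sample-size paragraph: α 0.05, power 80%, correlation 0.6, minimum 19. Sidedness is not stated; two-sided is assumed. For one independent pair per child, Fisher z gives

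n = ((1.960 + 0.842) / atanh(0.6))² + 3 = (2.802 / 0.6931)² + 3 = 19.34, which rounds up to 20.

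The t-based version with bias correction gives power of 78.4% at n = 18 and 80.9% at n = 19, hence 19. One-sided, n would be 16. So 19 can be reached without a repeat count or a within-child correlation, and the plan states neither. This suggests, but does not prove, that repeated measures played no part.

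**2. Does any unit of analysis rescue the tests?** The plan does not name one.
- *All accepted readings pooled* (the natural inference from the protocol): readings within a child are dependent, so both tests fail their assumption.
- *One mean per child per score*: the same child sits in several groups, so a one-way ANOVA is still wrong.

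**3. Size, by simulation.** The documents give 22 children and the six BIS bands. They do not give readings per child, intraclass correlation (ICC), serial correlation or time at each score, and the table of score levels is not shown. Assumed:
- 10, 20 or 30 readings per child; five score levels in time order, the top two being deep sedation.
- BIS = 70 + 15 × a standardised value, with ICC 0.3 or 0.5 and lag-1 autocorrelation 0 or 0.6.
- Time at each score equal, moderately uneven (SD across children 8 points around 20%) or strongly uneven (SD 16 points, the extreme case).

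This makes 3 × 3 × 2 × 2 = 36 settings of 1000 runs. As a control, with no ICC or autocorrelation and 20 readings, ANOVA rejected 4.3%–5.1% and Spearman 4.8%–5.7%.

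Rejection of a true null at nominal 5%:

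| Time at each score | ANOVA | Spearman |
|---|---|---|
| Equal | 0.1%–27% | 1%–18% |
| Moderately uneven | 1.5%–36% | 2%–21% |
| Strongly uneven | 10%–66% | 8%–33% |

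With one mean per child per score, ANOVA rejected 0%–1.1%. With six levels and 20 readings, pooled ANOVA rejected 0.5%–51% and Spearman 1%–23%. Other simulations of the same kind reached maxima of 45% (moderate) and 73% (strong) for ANOVA, so the upper ends are not sharp.

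A different data model, with equal ICC in both BIS and score and no autocorrelation, gave for ANOVA 4.6%–6.4% at ICC 0.1, 8.8%–21.7% at 0.3 and 23.8%–48.2% at 0.5. With BIS ICC 0.3 and no clustering in the score, both tests were near nominal (4.7%–5.4%).

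**4. When BIS does fall with score.** With a slope of −0.53 SD per level and five equally used levels (SD √2), 0.53 × √2 = 0.75 and 0.75 / √(1 + 0.75²) = 0.60, the plan's target in absolute value. Ratio of actual to reading-level standard error (empirical SD over Fisher z, DeLong or binomial):

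| Measure | Ratio |
|---|---|
| Pooled Spearman | 0.9–2.3 |
| AUC | 0.9–2.2 |
| Sensitivity, fixed cut-off | 1.2–2.5 |
| Specificity, fixed cut-off | 1.3–2.7 |

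The sensitivity and specificity ratios exceeded 1 in all 36 settings, including those where ANOVA was conservative. Reading-level 95% intervals, if reported, would cover 57%–89% (sensitivity) and 53%–88% (specificity). With 20 readings per child, the pooled Spearman's 95% sampling range runs from 0.53–0.66 (best) to 0.48–0.71 (worst).

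If BIS is equal at the two deepest levels, that contrast (nominal 0.05 / 10 pairs = 0.5%) is declared different in 0%–15% of studies.

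**5. Kappa.** For two observers, five levels, true kappa 0.75 and ICC of agreement 0.05–0.2, the standard error ratio is 1.2–2.6. At ICC 0.2 and 20 readings, estimates range over 0.65–0.84, against 0.70–0.80 for independent readings. The wider range spans the 0.7 threshold.

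**The case against.** The strongest reply is that little turns on the p values. The highest rejection rates assume BIS is unrelated to sedation, which nobody expects. At the planned correlation of 0.6, the weakest correlation in 4,800 simulated studies was still 0.39 in absolute value, so clustering does not overturn the main association. The plan does not say that readings are pooled. With one mean per child per score the ANOVA is conservative, so a significant result would stand. Every size input is assumed, and the largest figures come from the extreme case.

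Much of this is right about size. The overall association is probably safe, the loss of precision is moderate, and some settings show no inflation. It does not make the tests valid. Neither unit of analysis meets the ANOVA's assumptions; one can produce false positives and the other hides real differences between scores. The neighbouring-score contrasts remain exposed, and the results closest to the aim have no interval.

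Two narrower points stand. The kappa sentence is ambiguous about what is compared with what, and only a two-observer kappa was simulated. A within-child correlation also answers a different question from the pooled one: it removes between-child BIS differences that matter for a single cut-off, and it was higher in the simulation (0.64–0.79 against 0.60). It should not replace the pooled value.

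**Conclusion.** The concern holds and must be fixed before the ANOVA and Spearman p values are relied on. That the independence assumption fails follows from the protocol and SAP text and needs no assumed figure. Pooling of readings is inferred, but the ANOVA fails under per-child means as well.

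The size is illustrative and rests on the assumed readings per child, correlations and time at each score. The p values can err in either direction. The reading-level standard error ranges from about correct to about 2.3-fold too small for the pooled Spearman, and is 1.2- to 2.7-fold too small for sensitivity and specificity. For ROC and kappa the fault is a missing interval, not a wrong estimate.

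**What to change.** 1. Replace the one-way ANOVA with a linear mixed model: random child intercept and residuals serially correlated by actual minute, so that minutes lost to low signal quality count as gaps. Alternatively, use GEE with child-level robust errors and a small-sample correction. Keep the Bonferroni contrasts.
2. Report a within-child repeated-measures correlation as the main correlation, with the pooled Spearman beside it as a description with a child-level bootstrap interval. Say that the two answer different questions.
3. Give intervals for AUC, sensitivity, specificity, cut-off and kappa from a bootstrap of whole children, choosing the cut-off again in each resample. State that these estimates weight children by accepted readings and mix within- and between-child differences. Add a check that weights children equally.
4. State the unit of analysis for each statistic, say what kappa compares, and report accepted readings per child.

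In simulation the mixed model rejected a true null in 2.3%–8.3% of runs with 20% of minutes missing at random; its covariance form was correctly specified, a favourable case. Child-bootstrap coverage of nominal 95% intervals was 87%–95% (pooled Spearman), 88%–94% (within-child correlation), 87%–94% (AUC), 93%–98% (cut-off), 94%–99% (sensitivity and specificity with the cut-off re-chosen; 88%–95% at a fixed cut-off) and 90%–94% (kappa). GEE and the equal-weight check were not simulated. There is no gain where the reading-level interval was already adequate: for AUC with equal time and no serial correlation it covered 89%–96%.

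The cost is SAP wording and a reanalysis; the text is in the past tense, so no new data are needed. Intervals will usually be wider, and with 22 children the bootstrap under-covers slightly for most measures.
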